9.7.3 Effectiveness analysis

Effectiveness analysis will be performed on the effectiveness set.

Effectiveness analyses will be performed by subgroup based on demographics and baseline characteristics.

The standard descriptive statistical parameters (number of patients, mean, standard deviation, median, minimum, maximum, etc.) will be summarized.

The changes of the effectiveness outcomes from baseline will be compared in an exploratory sense via paired t-test.

For investigator's overall effectiveness evaluation, the number and percentage of patients will be presented. If the result of overall evaluation is 'improved', it will be classified as 'effective'. If the result of overall evaluation is 'unchanged' or 'aggravated', it will be classified as 'ineffective'.

'Effective' and 'ineffective' will be reported using numbers of patients, percentages with 95% CIs.

Categorical variable will be reported using numbers of patients, numbers of patients assessed as 'effective', effective rates and 95% CIs. Effectiveness will be analyzed by Pearson's chi-square test or Fisher's exact test to determine if there are statistically significant differences.

Continuous variable will be reported using numbers of patients. Odds ratio and 95% CIs by simple logistic regression will be summarized.

To estimate any factors that are thought to influence an effective rate, logistic regression analysis and/or poisson regression will be conducted, and for statistically significant covariates the meaning will be described.

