8.2 SECONDARY OBJECTIVE

The secondary objective is to monitor the effectiveness of Spesolimab IV by evaluating changes in the GPPGA pustulation sub-score (mandatory), GPPGA score (mandatory), GPPASI (if collected), pain VAS (if collected) and PSS (if collected) from baseline after 1 week and/or 4 weeks.

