9.3.2.2 Secondary outcomes

The secondary outcomes are the effectiveness outcomes as follows:

- A GPPGA pustulation sub-score of 0 indicating no visible pustules at Week 1
- A GPPGA pustulation sub-score of 0 indicating no visible pustules at Week 4
- A GPPGA score of 0 or 1 at Week 1
- A GPPGA score of 0 or 1 at Week 4

The GPPGA is provided in [Annex 4](#). It is a modified the Physician's Global Assessment (PGA), a physician's assessment of psoriatic lesions, which was adapted to the evaluation of GPP patients [[R15-5200](#)]. The investigator scores the erythema, pustules, and scaling of all GPP lesions from 0 to 4. Each component is graded separately, the average is calculated, and the final GPPA is determined from this composite score. A lower score indicates a lesser severity, with 0 being clear and 1 being almost clear.

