9.5 STUDY SIZE

The enrolment target is 21 patients for a total of 6 years, considering the prevalence of generalized pustular psoriasis with acute flares in Korea and the market conditions. [REDACTED] is committed to collecting data from all patients who receive Spesolimab IV within a 2-year period after the product's launch (complete enumeration).

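### The four secondary effectiveness outcomes are yes/no responses, but the only inferential method that could apply to them overall is a paired t-test on change from baseline, which does not fit them

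*Protocol*

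**What the plan says.** Section 9.3.2.2 presents the secondary outcomes as the effectiveness outcomes and lists four. Two are absence of visible pustules ("A GPPGA pustulation sub-score of 0 indicating no visible pustules at Week 1", repeated for Week 4). Two are a clear or almost clear overall score ("A GPPGA score of 0 or 1 at Week 1" and "A GPPGA score of 0 or 1 at Week 4"). Each is a state that a patient either has or does not have at a visit.

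Section 9.7.3 uses the same term, effectiveness outcomes, and states: "The changes of the effectiveness outcomes from baseline will be compared in an exploratory sense via paired t-test". The abstract carries the same sentence. Section 9.7.3 also lists general descriptive statistics (number of patients, mean, SD, median, range).

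A proportion with an interval does appear in that section: "Effective' and 'ineffective' will be reported using numbers of patients, percentages with 95% CIs". Those two categories are derived from the investigator's overall evaluation, which Section 9.3.2.3 classes as a further outcome. The chi-square or Fisher tests and the logistic or Poisson regressions that follow concern the same effective rate.

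Objective 8.2 says that effectiveness is monitored "by evaluating changes in the GPPGA pustulation sub-score (mandatory), GPPGA score (mandatory"), followed by GPPASI, pain VAS and PSS where collected. These are changes in scores, not responses.

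**The concern.** The secondary outcomes and the method named for effectiveness outcomes are of different kinds. A paired t-test estimates a mean within-patient change. The four outcomes call for the proportion of patients in a given state at a visit.

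The investigator's global judgement is given a percentage and an interval, although Section 9.9.2 itself warns that assessment criteria may differ between investigators. The four outcomes built on defined score thresholds are given neither. Section 7 says the results go to the regulator and are reflected in the approved information. In a single-arm study of 21 patients, the useful result is each response rate with a valid interval. A p-value against baseline does not supply that.

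**Working it through.** **Inputs.** From Section 9.5: "The enrolment target is 21 patients for a total of 6 years". The protocol derives no power, effect size or response rate for effectiveness, so there is no figure of its own to reproduce. Assumptions made here: all 21 patients are evaluable, and in steps 1 to 3 none is a responder at baseline.

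**Step 1: what the test becomes.** Code response as 1 and non-response as 0. With every baseline value 0, each paired difference equals the follow-up response. For x responders among n:

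- mean difference = x/n
- SD = √[(x/n)(1 − x/n)·n/(n − 1)]
- t = mean/(SD/√n) = √[x(n − 1)/(n − x)], with n − 1 = 20 degrees of freedom

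The null hypothesis is a response rate of exactly zero. A single responder already refutes that, so the p-value adds nothing useful.

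**Step 2: numbers at n = 21.** The exact McNemar p-value is min(1, 2 × 0.5^x), because all changes go one way.

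| Responders | Rate | t | t-test p | Exact McNemar p | Clopper-Pearson 95% CI |
|---|---|---|---|---|---|
| 0 | 0% | undefined | – | – | 0 to 16.1% |
| 1 | 4.8% | √(20/20) = 1.00 | 0.33 | 1 | 0.1 to 23.8% |
| 3 | 14.3% | √(60/18) = 1.83 | 0.083 | 0.25 | 3.0 to 36.3% |
| 4 | 19.0% | √(80/17) = 2.17 | 0.042 | 0.125 | 5.4 to 41.9% |
| 11 | 52.4% | √(220/10) = 4.69 | 0.00014 | 0.00098 | 29.8 to 74.3% |
| 21 | 100% | undefined | – | – | 83.9 to 100% |

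**Step 3: reading the table.** The t-test crosses 0.05 at 4 of 21 responders, where the exact paired test does not. At 0 or 21 responders the differences have zero variance and there is no test statistic. The exact interval exists in every row.

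**Step 4: some responders at baseline.** Section 9.2.2.2 requires a flare but sets no minimum score. Under Annex 4, GPPGA is 1 whenever the component mean is above 0 and below 1.5. Erythema 1, pustules 2 and scaling 1 give 4/3 = 1.33, hence GPPGA 1 with pustules present. A baseline GPPGA response is therefore not excluded by the entry criteria. Suppose 11 of 21 respond at follow-up (11/21 = 0.524) and b of them already met the response at baseline and kept it. The mean change is (11 − b)/21:

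- b = 1: 10/21 = 0.476
- b = 2: 9/21 = 0.429
- b = 3: 8/21 = 0.381

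The quantity tested is then no longer the response rate that Section 9.3.2.2 defines.

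**Step 5: the other reading.** Suppose the t-test sentence is meant only for the score changes in 8.2. The method then suits its target better, but the four secondary outcomes have no inferential method, and the objective and the outcome list still describe different quantities.

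**The case against.** The strongest reply is that the t-test sentence was never meant for the yes/no outcomes. It speaks of changes from baseline, and the abstract lists the effectiveness outcomes as changes in five scores, as 8.2 does. This is a fair reading and it stands as a possibility. It does not remove the point: Section 9.3.2.2 attaches the same term to four responses, and step 5 shows what this reading leaves open.

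A second reply is that details of intervals and displays belong in the SAP, which Section 9.7 announces and which is not at hand. Had the protocol been silent, that would settle the matter. It is not silent: it names a method, twice, under a term it has defined as the four responses.

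A reader might also infer more than the protocol supports:

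- **That the t-test is the only analysis planned for effectiveness.** It is not. Section 9.7.3 also names descriptive statistics and, for the overall evaluation, percentages with CIs, chi-square or Fisher tests and regression.
- **That the plan will publish wrong confidence limits.** No t-based interval is promised. If one were added, it would go wrong at the extremes (3/21: −2.0 to 30.6%, against exact 3.0 to 36.3%; 20/21: 85.3 to 105.2%, against 76.2 to 99.9%). Near one half it would almost agree with the exact interval (11/21: 29.1 to 75.7%, against 29.8 to 74.3%).
- **That baseline response is certainly zero.** This is plausible in a flare, but the entry criteria do not fix it.
- **That a paired t-test on the 0 to 4 scores is itself an error.** As an exploratory summary of mean change this is a matter of preference. Improvement without the drug is a limit of any single-arm design, whichever paired test is used.

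**Conclusion.** The point holds at moderate severity. On either reading of Section 9.7.3, the four outcomes in Section 9.3.2.2 lack a fitting inferential method, and objective 8.2 does not match them.

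The p-values rest on 21 evaluable patients and no responders at baseline. The mismatch between outcome type and method rests on neither assumption.

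A reader might take this as a defect that undermines the study. The documents do not support that: all analyses are declared exploratory, the primary objective is safety, and no decision rule, alpha or power depends on the effectiveness p-value.

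**What to change.** 1. In Section 9.7.3 and the abstract, state that each of the four secondary responses, and GPPASI 50 and 75 where collected, is reported as n/N with a 95% CI by a named method (Clopper-Pearson or Wilson), with no test against baseline.
2. Limit the exploratory paired comparison to changes in the numeric scores: GPPGA, pustulation sub-score, GPPASI, pain VAS and PSS.
3. Align objective 8.2 and the abstract's outcome list with Section 9.3.2.2, so that responses and score changes are each named and each tied to a method.

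The cost is protocol and SAP wording and table shells. No additional data are needed, because the GPPGA and pustulation sub-score are already mandatory at baseline, Week 1 and Week 4.

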9.7.4 Interim analysis

There will be interim analyses according to Korean regulations.

9.7.5 Handling of missing data

Maximum attempt will be made to ensure the completeness of data collection. All available data will be used in the data analysis. Missing or incomplete dates of AEs are imputed according to Boehringer Ingelheim standard.

9.8 QUALITY CONTROL

The quality control, review, and monitoring plan are summarized below. Greater details are documented in the DMP and PMP.

All entries in the Electronic Case Report Forms (eCRFs) and the existing coding will be stored in a database. The structure of the database is based on the division into sections and entry fields defined in the eCRFs. To improve and ensure data quality, data checks will be performed automatically in the eCRFs directly on electronic entry at the study site. Plausible value ranges for numerical data entries and logical data and list entries will be filed in the eCRFs. The tests for consistency and completeness based on this will be performed during entry in the eCRFs. The validity of the recorded data will therefore be ensured by the validations incorporated in the documentation system, which highlight incorrect or implausible entries to the data entry clerk / doctor.

All changes after initial data entry will be documented in an audit trail.

An additional inspection/quality assurance check of the data collected within this ONIS can be performed in case of any deviation.

9.9 LIMITATIONS OF THE RESEARCH METHODS

9.9.1 Lost to follow up

All efforts will be made to minimize loss to follow up, particularly in the tracking of lost patients. To the extent possible, occurrence of adverse event, at minimum, for patients lost to follow up will be obtained via patient visit / telephone / letter / email etc. This allows assessment of the impact of informative censoring due to treatment discontinuation.

9.9.2 Confounding

As in any observational study, confounding may affect the estimation of association between drug exposure and outcome of interest and statistical techniques. When the investigators assess the overall effectiveness, different assessment criteria among them may affect the study outcome. Also, information bias may occur and cause a distortion in the observed association due to a lack of accurate measurements of key study variables. If key study variables (exposure, health outcome, or confounders) are inaccurately measured or classified (which may happen in real-world clinical settings), bias in the risk ratio, rate ratio, or odds ratio can be produced.

9.10 OTHER ASPECTS

The protocol of this regulatory required ONIS will be submitted to MFDS for approval. Also, the protocol will be submitted to Institutional Review Board (IRBs) whenever required or requested by these study sites. This study will be conducted in accordance with the 「Standards for Re-examination of New Drugs, Etc.」 notified by MFDS, the Korean Pharmaceutical Affairs Code (KPAC), Enforcement Regulation of KPAC and other applicable local laws and industry code (including but not limited to the Regulations on Fair Competition in the Trade of Medicines of the Korea Pharmaceutical and Bio-Pharma Manufacturers Association (KPBMA) and the Korean Research-based Pharma Industry Association (KRPIA)).

████████████████████ will submit periodic reports during re-examination period, and the study final report to MFDS upon study completion. The periodic report for the final year will be substituted with the final report. When required, the interim reports and the final report will be submitted to the IRBs as well.

9.10.1 Data quality assurance

A quality assurance audit / inspection of this study may be conducted by the sponsor or sponsor's designees or by IRBs / Independent Ethics Committee (IECs) or by regulatory authorities. The quality assurance auditor will have access to all medical records, the investigator's study-related files and correspondence, and the informed consent documentation of this study.

9.10.2 Study records

CRFs for individual patients will be provided by the sponsor, either on paper or via remote data capture, if applicable.

9.10.2.1 Source documents

Source documents provide evidence for the existence of the patient and substantiate the integrity of the data collected. Source documents are filed at the investigator's site.

Data entered in eCRFs that are transcribed from source documents must be consistent with the source documents or the discrepancies must be explained. The investigator may need to request previous medical records or transfer records, depending on the study; also current medical records must be available.

For eCRFs **all** data must be derived from source documents.

9.10.2.2 Direct access to source data and documents

The investigator / institution will permit study-related monitoring, audits, IRB / IEC review and regulatory inspection, providing direct access to all related source data / documents. CRFs / eCRFs and all source documents, including progress notes and copies of laboratory and medical test results must be available at all times for review by the sponsor's clinical study monitor, auditor and inspection by health authorities (e.g. US Food and Drug Administration (FDA)). Boehringer Ingelheim study staff and auditor may review all CRFs / eCRFs, and written informed consents. The accuracy of the data will be verified by reviewing the documents described in Section [9.10.2.1](#).

10. PROTECTION OF HUMAN SUBJECTS

The study will be carried out in compliance with the protocol, the principles laid down in the Declaration of Helsinki, Guidelines for GPP, and the relevant Boehringer Ingelheim SOPs.

Standard medical care (prophylactic, diagnostic and therapeutic procedures) remains the responsibility of the treating physician of the patient.

The investigator should inform the sponsor immediately of any urgent safety measures taken to protect the study subjects against any immediate hazard, and also of any serious breaches of the protocol.

10.1 STUDY APPROVAL, PATIENT INFORMATION, AND INFORMED CONSENT

This ONIS will be initiated only after all required legal documentation has been reviewed and approved by the respective IRB / IEC and Competent Authority (CA) according to national and international regulations. The same applies for the implementation of changes introduced by amendments.

Prior to patient participation in the study, written informed consent must be obtained from each patient (or the patient's legally accepted representative) per GPP and according to the regulatory and legal requirements of the participating country, if applicable.

10.2 STATEMENT OF CONFIDENTIALITY

Individual patient medical information obtained as a result of this study is considered confidential and disclosure to third parties is prohibited with the exceptions noted below. Patient confidentiality will be ensured by using patient identification code numbers. Treatment data may be given to the patient's personal physician or to other appropriate medical personnel responsible for the patient's welfare. Data generated as a result of the study need to be available for inspection on request by the participating physicians, the sponsor's representatives, by the IRB / IEC and the regulatory authorities.

11. MANAGEMENT AND REPORTING OF ADVERSE EVENTS/ADVERSE REACTIONS

11.1 DEFINITIONS OF ADVERSE EVENTS

Adverse Event

An Adverse Event (AE) is defined as any untoward medical occurrence in a patient or clinical investigation subject administered a medicinal product and which does not necessarily have a causal relationship with this treatment. An AE can therefore be any unfavorable and unintended sign (e.g. an abnormal laboratory finding), symptom, or disease temporally associated with the use of a medicinal product, whether or not considered related to the medicinal product.

Adverse Drug Reaction

An Adverse Drug Reaction (ADR) is defined as a response to a medicinal product which is noxious and unintended. Response in this context means that a causal relationship between a medicinal product and an AE is at least a reasonable possibility. Adverse reactions may arise from use of the product within or outside the terms of the marketing authorization or from occupational exposure. Conditions of use outside the marketing authorization include off-label use, overdose, misuse, abuse and medication errors.

Serious Adverse event

A Serious Adverse Event (SAE) is defined as any AE which

- results in death,
- is life-threatening,
- requires in-patient hospitalization, or
- prolongation of existing hospitalization,
- results in persistent or significant disability or incapacity, or
- is a congenital anomaly / birth defect

Life-threatening in this context refers to a reaction in which the patient was at risk of death at the time of the reaction; it does not refer to a reaction that hypothetically might have caused death if more severe.

Medical and scientific judgement should be exercised in deciding whether other situations should be considered serious reactions, such as important medical events that might not be immediately life threatening or result in death or hospitalization but might jeopardize the patient or might require intervention to prevent one of the other outcomes listed above. Examples of such events are intensive treatment in an emergency room or at home for allergic bronchospasm, blood dyscrasias or convulsions that do not result in hospitalization or development of dependency or abuse. Any suspected transmission via a medicinal product of an infectious agent is also considered a serious adverse reaction.

Adverse Event of Special Interest

The term Adverse Event of Special Interest (AESI) relates to any specific AE that has been identified at the project level as being of particular concern for prospective safety monitoring and safety assessment within this study, e.g. the potential for AEs based on knowledge from other compounds in the same class.

The following are considered as AESIs:

- Systemic hypersensitivity reactions including infusion reactions and anaphylactic reactions
- Severe infection
- Opportunistic and mycobacterium tuberculosis infections

11.2 ADVERSE EVENT AND SERIOUS ADVERSE EVENT COLLECTION AND REPORTING

The investigator shall maintain and keep detailed records of all AEs in their patient files.

Collection of adverse events

The study is a non-interventional study in real-world situation and will be conducted within the conditions of the approved marketing authorization. For this reason, the following AE collection and reporting requirements have been defined.

All serious adverse events, non-serious adverse events and AESIs occurring from the signing date on data release consent form to the end of the study need to be collected, documented and reported to the sponsor using the AE page of eCRF.

The investigator carefully assesses whether an AE constitutes an ADR using the information below.

Causal relationship of adverse event

The definition of an adverse reaction implies at least a reasonable possibility of a causal relationship between a suspected medicinal product and an AE. An adverse reaction, in contrast to an AE, is characterized by the fact that a causal relationship between a medicinal product and an occurrence is suspected.

Medical judgment should be used to determine the relationship, considering all relevant factors, including pattern of reaction, temporal relationship, de-challenge or re-challenge, confounding factors such as concomitant medication, concomitant diseases and relevant history.

Arguments that may suggest a **reasonable causal relationship** could be:

- The event is consistent **with the known pharmacology** of the drug
- The event is known to be caused by or **attributed to the drug class**
- A **plausible time to onset of the event** relative to the time of drug exposure
- Evidence that the **event is reproducible** when the drug is re-introduced
- **No medically sound alternative etiologies** that could explain the event (e.g. preexisting or concomitant diseases, or co-medications).
- The event is typically **drug-related and infrequent in the general population** not exposed to drugs (e.g. Stevens-Johnson syndrome).
- An indication of dose-response (i.e. greater effect size if the dose is increased, smaller effect size if dose is diminished).

Arguments that may suggest that there is **no reasonable possibility of a causal relationship** could be:

- No plausible time to onset of the event relative to the time of drug exposure is evident (e.g. pre-treatment cases, diagnosis of cancer or chronic disease within days / weeks of drug administration; an allergic reaction weeks after discontinuation of the drug concerned)
- Continuation of the event despite the withdrawal of the medication, taking into account the pharmacological properties of the compound (e.g. after 5 half-lives). Of note, this criterion may not be applicable to events whose time course is prolonged despite removing the original trigger.
- Additional arguments amongst those stated before, like alternative explanation (e.g. situations where other drugs or underlying diseases appear to provide a more likely explanation for the observed event than the drug concerned).
- Disappearance of the event even though the study drug treatment continues or remains unchanged.

The causal relationship must be provided by the investigator for all potential study drugs, i.e. the Boehringer Ingelheim study drug and for all other study drugs. The reason for the decision on causal relationship needs to be provided in the eCRF and on the ONIS AE form (if applicable).

Related:

- a. **Certain:** An event occurring in a plausible time relationship to drug administration and that cannot be explained by concurrent disease or other drugs or chemicals. The response to withdrawal of the drug (dechallenge) should be clinically plausible. The event must be definitive pharmacologically or phenomenologically, using a satisfactory rechallenge procedure if necessary.
- b. **Probable/Likely:** An event with a reasonable time sequence to administration of the drug, unlikely to be attributed to concurrent disease or other drugs or chemicals, and which follows a clinically reasonable response on withdrawal (dechallenge). Rechallenge information is not required to fulfill this definition.
- c. **Possible:** An event with a reasonable time sequence to administration of the drug, but which could also be explained by concurrent disease or other drugs or chemicals. Information on drug withdrawal may be lacking or unclear.
- d. **Conditional/Unclassified:** Case of requiring more data or reviewing the additional data for the appropriate assessment

- e. Unassessable/Unclassifiable: Case that it cannot be judged and complemented or confirmed due to the insufficient or contradictory information

Unrelated:

- Unlikely: An event with a temporal relationship to drug administration which makes a causal relationship improbable, and in which other drugs, chemicals or underlying disease provide plausible explanations.

Intensity of adverse event

The intensity of the AE should be judged based on the following:

- Mild: Awareness of sign(s) or symptom(s) which is / are easily tolerated
Moderate: Enough discomfort to cause interference with usual activity
Severe: Incapacitating or causing inability to work or to perform usual activities

Pregnancy:

In rare cases, pregnancy might occur in a ONIS. Once a patient has been enrolled in the study and has taken study medication, the investigator must report any drug exposure during pregnancy in a study participant within 7 days by means of Part A of the Pregnancy Monitoring Form to the sponsor's unique entry point.

The outcome of the pregnancy associated with the drug exposure during pregnancy must be followed up and reported to the sponsor's unique entry point on the Pregnancy Monitoring Form (Part B).

The investigator site file (ISF) will contain the Pregnancy Monitoring Form (Part A and B). As pregnancy itself is not to be reported as an AE, in the absence of an accompanying AE, only the Pregnancy Monitoring Form and not the ONIS AE form is to be completed. If there is an AE associated with the pregnancy a ONIS AE form must be completed in addition.

Expedited Reporting of AEs and Drug Exposure during Pregnancy to Boehringer Ingelheim Patient Safety and Pharmacovigilance

The following must be reported by the investigator on the ONIS AE form ([Annex 8](#)) and / or Pregnancy Monitoring Form ([Annex 9](#)) from signing the informed consent onwards until the end of the study and provide Boehringer Ingelheim unique entry point:

Boehringer Ingelheim contact details

Local Patient Safety Lead (LPSL)

Tel: [REDACTED]

Fax: [REDACTED]

Address: [REDACTED]

Type of Report	Timeline
All SAEs	immediately within 24 hours
All protocol specified AESIs	Immediately within 24 hours
All non-serious AEs	7 calendar days
Drug exposure during pregnancy	7 calendar days

The same timelines apply if follow-up information becomes available for the respective events. In specific occasions the Investigator could inform the Sponsor upfront via telephone. This does not replace the requirement to complete the AE page of the eCRF and the ONIS AE form and report the ONIS AE form.

Information required

For each reportable AE, the investigator should provide the information requested on the appropriate (e)CRF page and the ONIS AE form.

The investigator should undertake all efforts to obtain and report the batch/lot number of the drug under study on the ONIS AE form.

